---	--

	
storage period. Results from the future use studies will not be shared with patients.
 
1) Safety Laboratory Assessments (Screening, Baseline, Days 21, 42, 63, 84, 105, 126 then every 42 days and EoT visit)
 
Blood samples of approximately 10 mL per visit for the assessment of hematological and serum chemistry parameters will be collected and processed in accordance with local laboratory procedures and reference ranges.
 
Safety laboratory panels are defined as follows:
 
Human immunodeficiency virus (HIV 1/2 antibodies), hepatitis B (HBsAg reactive) and hepatitis C (HCV ribonucleic acid [RNA] qualitative) (at screening only).
 
Hematology: Hematology to include CBC, including RBC count, hemoglobin, hematocrit, reticulocyte count, WBC count with differential (neutrophils, bands, eosinophils, basophils, lymphocytes, monocytes, and other cells), platelet count, C-reactive protein (CRP).
 
Serum Chemistry: BUN or urea, creatinine, sodium, chloride, potassium, magnesium, bicarbonate, calcium, phosphorus, total protein, albumin, alkaline phosphatase, glucose, total bilirubin, direct and indirect bilirubin, lactate dehydrogenase (LDH), cholesterol, uric acid, triglyceride levels, gamma glutamyl transpeptidase (GGT), AST, and ALT.
 
2) Exploratory Endpoint Laboratory Assessments (Baseline, Days 84 then every 84 days and EoT visit)
 
A 1 x 10 mL whole blood sample to assess vaccine-specific cytokine levels and in-vitro inhibition of tumor cell growth will be obtained from each patient at Days 0, 84 then every 84 days and at EoT visit. When vaccination with IMU-131 occurs, these samples will be taken prior to vaccination.
 
3) Immunologic Assessments
 
a) Humoral samples (Baseline, Days 21, 42, 63, 84, 126 then every 42 days and EoT visit)
 
A 1 x 10 mL whole blood sample for humoral immunity will be obtained from each patient at Days 0, 21, 42, 63, 84, 126 then every 42 days and at EoT visit. When vaccination with IMU-131 occurs, these samples will be taken prior to vaccination.
 
b) Cellular samples (Screening [Phase 2 Extension only], Baseline, Days 84 then every 84 days and EoT visit)
 
Collection of 40 mL blood sample will be performed for PBMC isolation and analysis of cellular parameters at Days 0, 84 then every 84 days and at EoT visit. When vaccination with IMU-131 occurs, these samples will be taken prior to vaccination.
 
In Phase 2 Extension, an additional 40 mL blood sample will be performed for PBMC isolation and analysis of cellular parameters during

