- B A 1 x 10 mL whole blood sample to assess vaccine-specific cytokine levels and in-vitro inhibition of tumor cell growth will be obtained from each patient at Days 0, 84 then every 84 days and at EoT visit.

Investigational Product: IMU-131
Protocol Identifier: IMU.ACS.001
Protocol Version: Protocol Global Amendment #5, 27 September 2023

- C 1 x 10 mL (i.e. 1 tube) whole blood sample for humoral immunity at Baseline, Days 21, 42, 63, 84, 126 then every 42 days and EoT visit and 40 mL blood sample at Screening (Phase 2 Extension only), Baseline, Days 84 then every 84 days and EoT visit for cellular immunity. To be taken prior to vaccination at Baseline visit.
- D Chemotherapy will be administered as a concomitant therapy to all patients as a 21-day regimen consisting of: cisplatin by intravenous administration at 80 mg/m² on the first day of each cycle and either 5-FU, 4000 mg/m² CIV (administered as 1000 mg/m²/day as continuous infusion for 96 hours on days 1 to 4 of each cycle) or capecitabine for 14 days at 2000 mg/m²/day, orally (administered as 1000 mg/m² twice daily morning and evening for a total of 2000 mg/m²/day on days 1 to 14 of each cycle), or capecitabine for 14 days at 2000 mg/m²/day, orally (administered as 1000 mg/m² twice daily morning and evening for a total of 2000 mg/m²/day on days 1 to 14 of each cycle) and oxaliplatin, by intravenous administration at 130 mg/m² on Day 1 of each cycle. Body weight to be measured and body surface area to be calculated based on weight and baseline height at the start of each 21-day chemotherapy cycle. Chemotherapy continues until ceased by the investigator as clinically indicated for the care of the patient. To document compliance while away from the clinic, patients will record capecitabine treatment in a patient diary.
- E Radiographic assessment to occur within 14 days prior to Baseline Visit, then at Days 42, 84, 126 every 42 days thereafter. Radiographic assessment continues until disease progression according to RECIST 1.1 response criteria, withdrawal or end of trial.
- F Chemotherapy continues for up to 6 cycles until disease progression or until ceased by the investigator as clinically indicated for the care of the patient, whichever occurs first.
- G Radiographic assessment according to RECIST 1.1 response criteria at post-treatment follow-up visit only for patients who have ended study treatment prior to disease progression.

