The visit window for Day 63 is +/- 7 days of the scheduled visit. Day 63 procedures should be performed in the following order:

- Blood sample for hematology and serum chemistry;
- Blood sample for humoral immunology;
- Weight, and vital signs (blood pressure, temperature and heart rate);
- Urine pregnancy test (female);
- Physical examination;
- Record concomitant treatments;
- Record adverse events;
- Initiate chemotherapy cycle 4.

6.4.8. Phase 2 and Phase 2 Extension Week 11/Day 77 (only for patients in IMU-131 plus chemotherapy cohorts)

The visit window for Day 77 is +/- 7 days of the scheduled visit. Day 77 procedures should be performed in the following order:

- Weight, and vital signs (blood pressure, temperature and heart rate);
- Urine pregnancy test (female);
- Administer IMU-131 vaccination;
- Record body temperature 30 (+/-10) minutes after vaccination;
- Record concomitant treatments;
- Record adverse events.

6.4.9. Phase 2 and Phase 2 Extension Week 12/Day 84 (Repeat every 12 weeks/84 days)

The visit window for Day 84 is +/- 7 days of the scheduled visit. Day 84 procedures should be performed in the following order:

- Weight, and vital signs (blood pressure, temperature and heart rate);
- Blood sample for hematology and serum chemistry;
- Blood sample for humoral and cellular immunology;
- Blood sample for exploratory endpoints;
- Urine pregnancy test (female);
- Physical examination;
- ECOG performance score;

Investigational Product: IMU-131
Protocol Identifier: IMU.ACS.001
Protocol Version: Protocol Global Amendment #5, 27 September 2023

- Cardiac assessment by echocardiography or MUGA scan and 12-lead ECG;
- Radiographic assessment;
- Optional tumor biopsy sample (at Day 84);
- Record concomitant treatments;
- Record adverse events;
- Initiate chemotherapy cycle 5.

6.4.10. Phase 2 and Phase 2 Extension Week 15/Day 105

The visit window for Day 105 is +/- 7 days of the scheduled visit. Day 105 procedures should be performed in the following order:

- Blood sample for hematology and serum chemistry;
- Weight, and vital signs (blood pressure, temperature and heart rate);
- Urine pregnancy test (female);
- Physical examination;
- Record concomitant treatments;
- Record adverse events;
- Initiate chemotherapy cycle 6.

6.4.11. Phase 2 and Phase 2 Extension Week 18/Day 126 (Repeat every 12 weeks/84 days)

The visit window for Day 126 is +/- 7 days of the scheduled visit. Day 126 procedures should be performed in the following order:

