## 4. General Statistical Considerations

### 4.1. Reporting Convention

### 4.2. Analysis Window

[figure not shown]
Baseline is defined as the last non-missing measurement prior to the first administration of any study treatment. For patients who were randomized but not treated, baseline will be the assessment taken on or before the randomization visit Baseline/ Day 0.

The day of the first dose of any study drug will be defined as study Day 0. Study day are calculated relative to Day 0, as the difference between the date of interest and Day 0.

[figure not shown]
For the post-baseline by-visit summaries of safety assessments, the nominal visits as captured on the eCRF page will be utilized.

For the purpose of by-visit summaries of efficacy assessment (like the change in tumor size) and humoral immunogenicity data, the post-baseline visit mapping rules described in [Table 4-1](#) and [Table 4-2](#) will be used respectively. When multiple records fall in the same post-baseline visit window, the record with the study day closest to the target visit day will be chosen. In a case of a tie, the record with the earlier date will be chosen. Records that not chosen will be effectively

treated similarly to an unscheduled assessment and will still be included in all except the by-visit summaries.

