#### 10.1.1. Time-adjusted Area Under Curve (AUC) of Her-2-specific Antibodies

[REDACTED]

Scatter plot to observe the relationship of time-adjusted AUC of Her-2-specific antibody from Baseline to Day 84 with change in tumor size from baseline to Day 84 will be presented.

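### The Week 11 booster window and the Week 12 sampling window overlap, so a compliant Day 84 antibody sample may be taken before or after the booster, and the visible SAP does not separate the two

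*Protocol*

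**What the plan says.** Protocol section 6.4.8 describes the Week 11 visit, held only for vaccinated patients, at which the fourth dose is given: "The visit window for Day 77 is +/- 7 days of the scheduled visit". Section 6.4.9 describes Week 12: "The visit window for Day 84 is +/- 7 days of the scheduled visit". Its procedures include "Blood sample for humoral and cellular immunology", the exploratory blood sample, a scan and the start of chemotherapy cycle 5. Table 3 shows the same windows.

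On the order of sampling and vaccination, the synopsis (Phase 2 and Phase 2 Extension Study Procedures) and section 8.6 both state: "When vaccination with IMU-131 occurs, these samples will be taken prior to vaccination". Table 3 footnote C ties this only to the first visit: "To be taken prior to vaccination at Baseline visit". Neither text sets a minimum interval between the Week 11 dose and the Week 12 sample.

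SAP section 4.2 maps humoral records to visits by study day counted from first treatment. When several records share a window, "the record with the study day closest to the target visit day will be chosen". SAP section 10.1.1 plots "time-adjusted AUC of Her-2-specific antibody from Baseline to Day 84" against the change in tumor size over the same period.

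**The concern.** On the nominal days the Day 84 sample comes 7 days after the fourth dose and should reflect the response to it. A sample taken on or before the booster day measures something else: the level left about 6 to 7 weeks after dose 3 (Days 77-84 less Day 35 is 42-49 days). If both kinds carry the same visit label, the Day 84 geometric mean titer has no single meaning.

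The AUC has a related problem. A pre-booster value is a true reading for that patient up to that day. But the difference from a patient sampled after the booster then comes from visit timing, not from response to the vaccine. That adds noise to the relation with tumor size, in a randomized vaccine arm of about 18 patients (36 randomized 1:1).

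The Day 84 visit matters because, apart from the End of Treatment visit, it supplies the only scheduled post-baseline cellular and exploratory samples before Day 168.

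**Working it through.** The documents state no booster-to-sample interval, so there is no figure to reproduce. The inputs are the target days and tolerances in Table 3 and section 6.4.

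**Step 1: windows.** Each window is target day ± tolerance, and the gap is sample day minus dose day. Later pairs follow from the repeat rules: doses at 140 + 63 = 203 and 140 + 3 × 63 = 329; samples at 126 + 84 = 210 and 84 + 3 × 84 = 336.

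| Dose | Sample | Dose window | Sample window | Shared days | Permitted gap (days) |
|---|---|---|---|---|---|
| 14 ± 3 | 21 ± 3 | 11-17 | 18-24 | none | +1 to +13 |
| 35 ± 3 | 42 ± 3 | 32-38 | 39-45 | none | +1 to +13 |
| 77 ± 7 | 84 ± 7 | 70-84 | 77-91 | 77-84 | -7 to +21 |
| 203 ± 7 | 210 ± 7 | 196-210 | 203-217 | 203-210 | -7 to +21 |
| 329 ± 7 | 336 ± 7 | 322-336 | 329-343 | 329-336 | -7 to +21 |

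The first two pairs always put the sample after the dose. That order is lost when the tolerance widens to ± 7 while the nominal gap stays at 7 days.

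**Step 2: count the permitted day-pairs for Day 77/84.** There are 15 × 15 = 225. The number with gap g is 15 - |g - 7|.

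- Sample before booster (g = -7 to -1): 1 + 2 + ... + 7 = 28.
- Same day (g = 0): 8, which are pre-booster under the synopsis rule.
- On or before the booster: 28 + 8 = 36, and 36/225 = 16%.
- Gap 4 to 10 days: 12 + 13 + 14 + 15 + 14 + 13 + 12 = 93, and 93/225 = 41%.

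**Step 3: how the share depends on the visit-day distribution.** The documents give none, so each line is an assumption.

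- Uniform and independent days: 16%.
- Triangular weights, 8 - |day - target|: 330/4096 = 8%.
- Uniform, but with Week 12 never before Day 84 because cycle 5 is on time or late: 15 × 8 = 120 pairs, of which only Day 84/Day 84 is pre-booster, so 1/120 = 0.8%.
- Both visits held on one day: every such sample is pre-booster.

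**Step 4: possible effect on the Day 84 geometric mean titer.** The documents give no booster fold-rise. Suppose it is k, all post-booster samples show it in full, and a share p is pre-booster. The ratio to the all-boosted mean is then k^(-p). With k from 2 to 5, assumed only for illustration:

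- p = 0.16: 0.90 to 0.77.
- p = 0.08: 0.95 to 0.88.
- p = 1/120: 0.99 at either end.

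The effect thus ranges from negligible to about a quarter, depending on quantities the documents do not give.

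**The case against.** The strongest reply is that the overlap exists on paper but will seldom matter. Protocol section 6 makes the investigator responsible for keeping visit intervals, and no text provides for combining Weeks 11 and 12. Of the 36 pairs, 28 need Week 12 to come before Week 11. Cycle 5 holds the Week 12 visit near Day 84. All of this stands as to frequency, and a reader should not take 16% as the expected rate. It does not remove the gap: section 6 counts only missed or out-of-window visits as deviations, so a same-day visit on any of Days 77-84 is compliant.

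Three stronger readings are tempting but unsupported.

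- *A false difference between the 100 and 200 microgram cohorts.* Nothing suggests that visit timing differs by cohort. The SAP covers the randomized Phase 2 only. Escalation is decided after Day 35, and Extension analysis is triggered by Day 42 completion or end of trial (sections 10.5, 10.6 and 10.6.2).
- *All immunology data pooled regardless of booster status.* This is visible for humoral data only. Cellular, serum-marker and in-vitro analyses are documented outside this SAP, and SAP Table 4-2 and parts of sections 10.1 and 10.1.1 cannot be seen.
- *The Day 84 AUC drives the PFS and OS correlations.* SAP section 12 lists antibody correlations with PFS and OS but names no day for them. The visible text ties the Day 84 AUC to tumor size alone.

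**Conclusion.** The point holds as a limited weakness of design and analysis. The permitted gap of -7 to +21 days follows from the protocol's own windows and needs no assumption. The rule in the synopsis and section 8.6 settles the same-day case as pre-booster, and the visible SAP has no step that separates such samples from post-booster ones.

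The share of patients affected is not known, and the 16% is probably too high for the reasons above. The size of any distortion cannot be given without a booster fold-rise. Immunogenicity is exploratory in both the randomized Phase 2 and the Extension, so the primary and secondary efficacy analyses and the safety analyses are unaffected. Control patients have no Week 11 visit and are not involved. The conclusion on humoral analysis would change if a hidden part of the SAP already uses time since vaccination.

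**What to change.** **Analysis (SAP sections 4.2 and 10.1).** For each vaccine-arm sample derive days since last vaccination from the recorded dates. Flag Day 84, Day 210 and Day 336 samples taken on or before the booster, and report them separately as pre-booster. Repeat the Day 84 summary and the AUC correlations without them, or adjusted for days since vaccination. This costs one derived variable and one repeat analysis, needs no new samples, and also covers patients already sampled.

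**Sampling still to come (Table 3 footnotes B and C, section 8.6).** State that Week 12 samples in vaccinated patients are drawn at least 1 day after the actual Week 11 vaccination and within the existing Day 77-91 window, and likewise at Days 210 and 336. This always fits: the latest permitted booster, on Day 84, still leaves Days 85-91. The vaccination windows are unchanged. The downside is that Weeks 11 and 12 can no longer be completed on one day. A patient boosted on the day cycle 5 starts would need a later blood draw.

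**Passages to reconcile.**

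- Footnote C limits pre-vaccination sampling to Baseline, while the synopsis and section 8.6 apply it whenever vaccination occurs.
- For the Extension, the synopsis (Dose and Schedule) and section 5.2.3 give Days 0, 14 and 35 and then every 63 days, which read literally makes the next dose 35 + 63 = Day 98. The synopsis (Study drugs) and section 6.4.8 have Day 77. What an Extension Day 84 sample represents depends on which applies.

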	
progression-free survival (PFS), time to progression (TTP), disease control rate (DCR), objective response rate (ORR), duration of objective response (DOR) and change in tumor size (CTS) according to Response Evaluation Criteria In Solid Tumors version 1.1 (RECIST 1.1) for the progression evaluation of radiographic data.
 
• To evaluate the safety profile of IMU-131 plus chemotherapy compared to chemotherapy alone.
	
Phase 2 Exploratory Objectives:
 
• To evaluate humoral and cellular immunogenicity data of IMU-131 plus chemotherapy compared to chemotherapy alone including P467-specific antibodies (IgG), Her-2-specific antibodies (IgG), vaccine-specific cytokine levels and regulatory and effector T and B cells.• To evaluate the arm-specific associations between clinical outcome, intra-tumor T cells, regulatory and effector T and B cells, and serum and biochemical markers of tumor progression.• To evaluate arm-specific associations between clinical outcome and HER2 and PD-L1 expression in tumor tissue.• To evaluate inhibition of in-vitro tumor cell growth and intracellular signaling processes by Her-2-specific antibodies (IgG)
	
Phase 2 Dose Escalation Primary Objective:
 
• To evaluate the safety and tolerability of 100μg and 200μg of IMU-131 in combination with chemotherapy.
	
Phase 2 Dose Escalation Secondary Objectives:
 
• To evaluate efficacy of IMU-131 plus chemotherapy including OS, PFS, TTP, ORR, DOR, DCR, and CTS according to Response Evaluation Criteria In Solid Tumors version 1.1 (RECIST 1.1) for the progression evaluation of radiographic data.
	
Phase 2 Dose Escalation Exploratory Objectives:
 
• To evaluate humoral and cellular immunogenicity data of IMU-131 plus chemotherapy compared to chemotherapy alone including P467-specific antibodies (IgG), Her-2-specific antibodies (IgG), vaccine-specific cytokine levels and regulatory and effector T and B cells.• To evaluate associations between clinical outcome, intra-tumor T cells, regulatory and effector T and B cells, and serum and biochemical markers of tumor progression.• To evaluate associations between clinical outcome and HER2 and PD-L1 expression in tumor tissue.• To evaluate inhibition of in-vitro tumor cell growth and intra-

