- H Cardiac assessment will be based on assessment of medical history, physical examination, 12-lead ECG results and evaluation LVEF by echocardiography or MUGA scan at Screening, Days 84 then every 84 days and at EoT visit.
- I No tumor biopsy is required if a previous pathology result or archival tissue is available confirming HER2/neu expression consistent with Inclusion Criteria #6.
- J Optional Day 84 and post-progression tumor biopsy (which may be provided at any time post progression).
- K Visit only for 'IMU-131 plus chemotherapy' group.
- L Record temperature 30min (+/- 10mins) after each IMU-131 vaccination.
- M Local laboratory testing. Safety lab samples can be drawn up to 72 hours before any on-study clinic visit.
- N A targeted, symptom directed physical examination may be performed at visits occurring after the Baseline Visit.
- O When progressive disease or withdrawal from study has been confirmed, EoT visit will be conducted at least 28 Days (+/- 7) after last dose of study medication. AEs to be checked at least 28 days after last study treatment per [Section 9.2: Reporting Period](#).
- P Phase 2 Extension only: Screening 40 mL cellular immunity blood sample after enrolment eligibility including HER2 over-expression is confirmed.
- Q Phase 2 only: Phase 2 Extension patients will no longer complete Post Treatment Follow Up Visits

Investigational Product: IMU-131
Protocol Identifier: IMU.ACS.001
Protocol Version: Protocol Global Amendment #5, 27 September 2023

R R End of trial is defined as 28 days post the last patient completing the end of treatment visit.

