- Record adverse events;
- Initiate chemotherapy cycle 1.

6.4.3. Phase 2 and Phase 2 Extension Week2/Day 14 (only for patients in IMU-131 plus chemotherapy cohorts)

The visit window for Day 14 is +/- 3 days of the scheduled visit. Day 14 procedures should be performed in the following order:

- Weight, and vital signs (blood pressure, temperature and heart rate);
- Urine pregnancy test (female);
- Administer IMU-131 vaccination;
- Record body temperature 30 (+/-10) minutes after vaccination;

Investigational Product: IMU-131
Protocol Identifier: IMU.ACS.001
Protocol Version: Protocol Global Amendment #5, 27 September 2023

- Record concomitant treatments;
- Record adverse events.

6.4.4. Phase 2 and Phase 2 Extension Week 3/Day 21

The visit window for Day 21 is +/- 3 days of the scheduled visit. Day 21 procedures should be performed in the following order:

- Blood sample for hematology and serum chemistry;
- Blood sample for humoral immunology;
- Weight, and vital signs (blood pressure, temperature and heart rate);
- Urine pregnancy test (female);
- Physical examination;
- Record concomitant treatments;
- Record adverse events;
- Initiate chemotherapy cycle 2.

6.4.5. Phase 2 and Phase 2 Extension Week 5/Day 35 (only for patients in IMU-131 plus chemotherapy cohorts)

The visit window for Day 35 is +/- 3 days of the scheduled visit. Day 35 procedures should be performed in the following order:

- Weight, and vital signs (blood pressure, temperature and heart rate);
- Urine pregnancy test (female);
- Administer IMU-131 vaccination;
- Record body temperature 30 (+/-10) minutes after vaccination;
- Record concomitant treatments;
- Record adverse events.

6.4.6. Phase 2 and Phase 2 Extension Week 6/Day 42

The visit window for Day 42 is +/- 3 days of the scheduled visit. Day 42 procedures should be performed in the following order:

- Blood sample for hematology and serum chemistry;
- Blood sample for humoral immunology;
- Weight, and vital signs (blood pressure, temperature and heart rate);
- Urine pregnancy test (female);
- Physical examination;
- Radiographic assessment;
- Record concomitant treatments;

Investigational Product: IMU-131
Protocol Identifier: IMU.ACS.001
Protocol Version: Protocol Global Amendment #5, 27 September 2023

- Record adverse events;
- Initiate chemotherapy cycle 3.

6.4.7. Phase 2 and Phase 2 Extension Week 9/Day 63

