- Blood sample for hematology and serum chemistry;
- Blood sample for humoral immunology;
- Weight, and vital signs (blood pressure, temperature and heart rate);
- Urine pregnancy test (female);
- Physical examination;
- Radiographic assessment;
- Record concomitant treatments;
- Record adverse events;

6.4.12. Phase 2 and Phase 2 Extension Week 20/Day 140 (Repeat every 9 week/63 days - only for patients in IMU-131 plus chemotherapy cohorts)

The visit window for Day 140 is +/- 7 days of the scheduled visit. Day 140 procedures should be performed in the following order:

- Weight, and vital signs (blood pressure, temperature and heart rate);

Investigational Product: IMU-131
Protocol Identifier: IMU.ACS.001
Protocol Version: Protocol Global Amendment #5, 27 September 2023

- Urine pregnancy test (female);
- Administer IMU-131 vaccination;
- Record body temperature 30 (+/-10) minutes after vaccination;
- Record concomitant treatments;
- Record adverse events.

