8.1. Assessments via Telemedicine

Telemedicine uses advanced telecommunication technologies to exchange health information and provide health care services across geographic, social, and other barriers. Where circumstances allow, and where additional flexibility is required due to restricted patient access to the study clinic or personnel, telemedicine technology may be used to collect study data to supplement study assessments. For example, visits may be conducted over several days within each visit window, with suitable assessments being completed using telemedicine technology with the remaining assessments being completed during a physical clinic visit. Examples of study assessments which may be completed using telemedicine technology include documenting concomitant treatments and adverse events, ECOG performance grade, and survival follow-up.

Investigational Product: IMU-131
Protocol Identifier: IMU.ACS.001
Protocol Version: Protocol Global Amendment #5, 27 September 2023

8.2. Phase 2 and Phase 2 Extension Physical Examination (Screening, Baseline, Days 21, 42, 63, 84, 105, 126 then every 42 days and EoT visit)

The physical examination will include an evaluation of body systems (e.g. cardiovascular, gastrointestinal, neurological, head and neck, respiratory, dermatology). After the Baseline physical examination, a symptom-directed physical examination is allowed at subsequent visits at the investigator's discretion.

8.3. Phase 2 and Phase 2 Extension Height, Weight, Vital Signs, Concomitant Medications, Concomitant Procedures and Adverse Events (at each study visit, excluding post-treatment follow-up visits)

Body height (at screening visit only), weight, and vital signs (blood pressure, pulse and temperature) will be measured and concomitant medications, concomitant procedures and adverse events will be documented.

8.4. Phase 2 and Phase 2 Extension Radiographic Assessment (Baseline, Days 42, 84, 126 then every 42 days)

For all patients a radiographic assessment will be performed at Baseline (assessment allowed up to 14 days before Baseline Visit), Days 42, 84, 126 then every 42 days until disease progression. Assessment of the tumor will include evaluation according to RECIST 1.1.

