8.6. Phase 2 and Phase 2 Extension Laboratory Assessments

Hematology and serum chemistry analyses will be performed by an accredited local laboratory. Serum predication markers of tumor progression and intra-tumor T cell and biomarker analysis will be performed by an accredited central laboratory. Humoral and cellular immunological analysis will be performed by an accredited specialist central immunology laboratory.

Unused blood /serum and/or tissue samples collected during the study from patients who have signed an appropriate informed consent form may be stored and used for future research. The coded samples may be stored up to 15 years after the clinical study ends. A patient may contact the investigator to have their unused samples destroyed at any time

Investigational Product: IMU-131
Protocol Identifier: IMU.ACS.001
Protocol Version: Protocol Global Amendment #5, 27 September 2023

during the storage period. Results from the future use studies will not be shared with patients.

1) Safety Laboratory Assessments (Screening, Baseline, Days 21, 42, 63, 84, 105, 126 then every 42 days and EoT visit)

Blood samples of approximately 10 mL per visit for the assessment of hematological and serum chemistry parameters will be collected and processed in accordance with local laboratory procedures and reference ranges.

Safety laboratory panels are defined as follows:

Human immunodeficiency virus (HIV 1/2 antibodies), hepatitis B (HBsAg reactive) and hepatitis C (HCV ribonucleic acid [RNA] qualitative) (at screening only).

Hematology: Hematology to include CBC, including RBC count, hemoglobin, hematocrit, reticulocyte count, WBC count with differential (neutrophils, bands, eosinophils, basophils, lymphocytes, monocytes, and other cells), platelet count, and C-reactive protein (CRP).

Serum Chemistry: BUN or urea, creatinine, sodium, chloride, potassium, magnesium, bicarbonate, calcium, phosphorus, total protein, albumin, alkaline phosphatase, glucose, total bilirubin, direct and indirect bilirubin, lactate dehydrogenase (LDH), cholesterol, uric acid, triglyceride levels, gamma glutamyl transpeptidase (GGT), AST, and ALT.

2) Exploratory Endpoint Laboratory Assessments (Baseline, Days 84 then every 84 days and EoT visit)

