9. ADVERSE EVENT REPORTING

9.1. Adverse Events

All observed or volunteered AEs regardless of treatment group or suspected causal relationship to the investigational product(s) will be reported as described in the following sections. All AEs will be collected in response to a general question about the subject's well-being and any possible changes from the baseline or previous visit, but shall not be specifically solicited with respect to particular AEs.

For all AEs, the investigator must pursue and obtain information adequate both to determine the outcome of the AE and to assess whether it meets the criteria for classification as an SAE requiring immediate notification to Imugene Limited or its designated representative. For all AEs, sufficient information should be obtained by the investigator to determine the causality of the AE. The investigator is required to assess causality. AEs will be followed until resolved, stable, or until the subject's last study visit or lost to follow-up. If an AE is not resolved or stabilized at the subject's last visit, it is up to the discretion of the investigator and the Sponsor's medical monitor to determine if further monitoring of the event is warranted.

As part of ongoing safety reviews conducted by the Sponsor, any non-serious adverse event that is determined by the Sponsor to be serious will be reported by the Sponsor as an SAE. To assist in the determination of case seriousness further information may be requested from the investigator to provide clarity and understanding of the event in the context of the clinical trial.

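### Adverse events are asked about more often in the IMU-131 arm than in the control arm of Phase 2, so recorded low-grade, transient TEAEs may be higher there even if true toxicity is equal

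*Protocol*

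**What the plan says.** - **Who attends.** Protocol Table 3 footnote K, repeated in SAP Appendix 1, labels the Week 2, 5, 11 and 20 visits "Visit only for 'IMU-131 plus chemotherapy' group". Protocol 6.4.3 is headed "Week2/Day 14 (only for patients in IMU-131 plus chemotherapy cohorts"; 6.4.5 (Day 35) and 6.4.8 (Day 77) carry the same restriction; 6.4.12 is headed "Week 20/Day 140 (Repeat every 9 week/63 days - only for patients in IMU-131 plus chemotherapy cohorts". Each lists vital signs, concomitant treatments and adverse events.
- **Common visits.** Safety laboratory tests and physical examinations are scheduled at "Screening, Baseline, Days 21, 42, 63, 84, 105, 126 then every 42 days and EoT visit" (Protocol 8.2 and 8.6), the same days in both arms. Neither is scheduled at the vaccine-only visits.
- **How events are elicited.** Protocol 9.1: "All AEs will be collected in response to a general question about the subject's well-being". The sentence goes on to cover changes since baseline or the previous visit. Protocol 9.11 adds observed and spontaneous reports.
- **What is compared.** A Phase 2 secondary objective is "To evaluate the safety profile of IMU-131 plus chemotherapy compared to chemotherapy alone". Concomitant medication use is also a safety endpoint.
- **How it is tabulated.** SAP 9.1 gives, by arm, the number of patients with each TEAE (each counted once) and the number of occurrences. Protocol 10.4.3 adds incidence adjusted for treatment duration. No readable text adjusts for contact frequency or limits a table to common visits.

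**The concern.** An open, non-directed question finds what the patient remembers. If one arm is asked more often, mild events that come and go between visits are more likely to be recorded there. The timing adds to this. With chemotherapy starting on Day 0, Days 14, 35 and 77 are day 15 of cycles 1, 2 and 4, just after a 14-day capecitabine course. The IMU-131 arm is asked then; the control arm is asked a week later.

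At stake is the reading of the by-arm TEAE tables. An excess of low-grade events could be put down to IMU-131 when part of it reflects how often patients were asked. The trial is small: SAP 9.1 calls a preferred term most frequent from 5% overall, and 5% of 36 patients is 1.8, so two patients are enough. A few extra reports can change that table.

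**Working it through.** The plan gives no figure for this, so there is none to reproduce.

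**Step 1: count contacts** (Protocol Table 3 and 6.4.2 to 6.4.12; patient on schedule).
- Control, after baseline to Day 126: Days 21, 42, 63, 84, 105, 126 = 6.
- IMU-131: the same six plus Days 14, 35, 77 = 9.
- Mean gap: 126/6 = 21 days v 126/9 = 14 days. To Day 140: 6 v 10.

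**Step 2: gaps between contacts to Day 126.**
- Control: six gaps of 21 days.
- IMU-131: 14, 7, 14, 7, 21, 14, 7, 21, 21 days, that is three each of 7, 14 and 21.

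**Step 3: share of episodes captured.** Assumption, not in the documents: onsets are uniform over Days 0 to 126, and an episode is recorded only if a contact falls within w days of onset, where w is its duration plus the time it is remembered. Then captured share = sum of min(w, gap) / 126.

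| w (days) | Control | IMU-131 | Ratio |
|---|---|---|---|
| 7 | 42/126 = 33% | 63/126 = 50% | 1.50 |
| 10 | 60/126 = 48% | 81/126 = 64% | 1.35 |
| 14 | 84/126 = 67% | 105/126 = 83% | 1.25 |
| 18 | 108/126 = 86% | 117/126 = 93% | 1.08 |
| 21 or more | 100% | 100% | 1.00 |

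For w of 7 or less no gap is shorter than w, so the ratio is simply 9/6 = 1.5. That is the model's ceiling.

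**Step 4: a gentler recall model.** Assume instead that an event is reported at the next contact with probability 0.5^(delay/h). The ratio to Day 126 is 1.21 at h = 7 days, 1.11 at 14, 1.06 at 28, 1.03 at 56, and 1.00 with no recall loss.

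**Step 5: patients rather than episodes.** Steps 3 and 4 count episodes. Suppose a toxicity recurs once per cycle for six cycles, captured independently, under the Step 3 model.
- w = 7, control: each cycle captured with probability 1/3, so incidence = 1 − (2/3)^6 = 91%.
- w = 7, IMU-131: probability 2/3 in cycles 1, 2 and 4 and 1/3 in cycles 3, 5 and 6, so incidence = 1 − (1/3)^3 × (2/3)^3 = 99%. The ratio is 1.08.
- w = 14: 99.9% v 100%.

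For an event that occurs once, the Step 3 ratios apply in full.

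**Step 6: where this effect ends.** TEAEs close 30 days after the last administration (SAP 9.1). With six cycles, a control patient's last dose is Day 105 (intravenous) to Day 118 (capecitabine, 105 + 13), so the window closes between Day 135 and Day 148. Vaccine visits from Day 203 onwards fall after that.

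**The case against.** The best reply is that both arms are asked about the whole interval. The question covers "a general question about the subject's well-being and any possible changes from the baseline or previous visit", so a control patient at Day 21 is asked about all of Days 0 to 21, and spontaneous reports and unscheduled visits also count. This stands in part. It makes capture equal only if nothing is forgotten over 21 days, which the documents neither assert nor rule out.

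Second, the tables least open to this problem are already planned: serious, fatal and Grade 3 or higher TEAEs by arm, and laboratory results from common visit days. That also stands, and it limits the point to low-grade, transient events. The duration-adjusted rates do not answer it, because they correct time at risk and not frequency of asking.

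Third, the extra visits are needed to give the vaccine. Agreed; nothing here would remove them.

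A reader might go further and infer any of the following. The documents do not support them.
- *That the TEAE comparison is inflated.* The documents establish unequal questioning, not a measured excess.
- *That the ratio of 1.5 applies to the patient percentages.* It is a ratio of episodes at the shortest recall examined; SAP 9.1 counts a patient once per event.
- *That the visits every 63 days after Day 140 add to the same bias.* From about Day 148 the control TEAE window has normally closed, so later differences come from the window, a separate matter.

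**Conclusion.** The asymmetry is certain: 9 v 6 post-baseline contacts to Day 126, and 10 v 6 to Day 140. The likely direction of any effect is towards more recorded low-grade, transient TEAEs in the IMU-131 arm, most of all in event counts. The size is uncertain, from no effect when recall reaches 21 days to an episode ratio of 1.5 at 7 days, and both recall models are assumptions. Grade 3 or higher and serious events should be much less affected, and scheduled laboratory tests fall on the same days in both arms. The point concerns randomised Phase 2 only, since the Extension has a single arm. It is a cheap improvement to the safety comparison and does not put the efficacy analysis in question.

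**What to change.** 1. **Protocol Table 3.** For any control patient still on schedule, add an adverse-event and concomitant-medication contact by telephone or telemedicine at Days 14, 35, 77 and 140 only. Protocol 8.1 already says that assessments which "may be completed using telemedicine technology include documenting concomitant treatments and adverse events". Cost: about four short calls per control patient.
2. **SAP 9.1.** Keep the full TEAE tables. State the unequal contact schedule, and that between-arm safety conclusions rest mainly on serious TEAEs, Grade 3 or higher TEAEs and the equally scheduled laboratory data. Add one supplementary by-arm table, to about Day 126, of Grade 1-2 TEAEs whose onset and end dates show them ongoing at a common visit (Days 21, 42, 63, 84, 105, 126).
3. **Safeguard for that table.** Do not filter out injection-site reactions or TEAEs reported as related to IMU-131; report them in full separately. Without this, the filter would hide short vaccine reactions. Protocol 1.3 describes Grade 1 redness and itch starting 3 days after a third injection and gone the next day. After a Day 35 dose that is Days 38 to 39, before the Day 42 visit.

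The table uses dates already collected. It loses some genuine short low-grade events, but only in the supplementary display. The synopsis rationale already cites safety data from the 36-patient Phase 2 study, so few or no control patients may remain on schedule. If control follow-up has ended, only items 2 and 3 apply.
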